	Days -28 to -1	Day 1 ^c	Day 8 for Part D1 only (± 1 day)	Day 15 (± 2 days)	Day 29 (± 2 days)	Period 2 Visit ^d		
Informed consent	X							
Randomization ^e		X						
Demographics	X							
Medical history	X							
CFQ-R ^{f,g}		X		X	X			
Weight ^h	X	X	X	X	X		X	
Height ^h	X							
Vital signs ⁱ	X	X	X	X	X	X	X	
Pulse oximetry ⁱ	X	X	X	X	X	X	X	

^a All assessments will be performed before dosing, unless noted otherwise. Assessments that are collected before and after dosing will only be collected once if study drug is not administered on the day of the visit (i.e., if subject prematurely discontinued study drug treatment).

^b If the subject prematurely discontinues study drug treatment, an ETT Visit should be scheduled as soon as possible after the decision to terminate study drug treatment. Subjects who prematurely discontinue treatment will be required to complete the Safety Follow-up Visit. If the ETT Visit occurs 3 or more weeks after the last dose of study drug, the ETT Visit will replace the Safety Follow-up Visit, and a separate Safety Follow-up Visit will not be required.

^c To be eligible to continue into the Treatment Period, subjects must have stable CF disease and have remained on stable CF medication regimen during the 28 days before the Day 1 Visit AND must not have had an acute non-CF illness within 14 days before the Day 1 Visit. See [Section 9.1.2.4](#).

^d The Period 2 Visit will occur 6 to 10 days after the actual date of the Day 29 Visit.

^e Randomization may occur on the previous day (Day -1 Visit) after all inclusion and exclusion criteria have been confirmed.

^f CFQ-R must be completed before the start of any other assessments scheduled at that visit.

^g The predose assessment on the Day 1 Visit may be performed on the previous day (Day -1 Visit) if randomization has occurred.

^h Weight and height will be measured with shoes off.

ⁱ Vital signs and pulse oximetry will be collected after the subject has been seated for at least 5 minutes.

Table 3-6 Study VX16-445-001: Schedule of Assessments for Parts D1 and D2

Event/Assessment ^a	Screening	Treatment Period					ETT Visit ^b	Safety Follow-up 28 (± 7) Days After Last Dose
		Period 1			Period 2			
	Days -28 to -1	Day 1 ^c	Day 8 for Part D1 only (± 1 day)	Day 15 (± 2 days)	Day 29 (± 2 days)	Period 2 Visit ^d		
Physical examination ^j	Complete	Abbrev.		Abbrev.	Abbrev.		Abbrev.	Complete
Standard 12-lead ECG ^k	X	X	X	X	X		X	X
Sweat chloride ^{g,l}	X	X	X	X	X	X ^m	X	X

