Spirometry ⁿ	X ^o	X	X	X	X	X ^m	X	X
Urinalysis ^g	X	X	X	X	X		X	X
Pregnancy test (all females of childbearing potential)	Serum	Urine			Urine		Serum	Serum
CFTR genotype ^p	X							
FSH ^q	X							
G6PD activity test ^r	X							

^j Complete and abbreviated PEs are described in [Section 11.7.3](#). Symptom-targeted PEs will occur at any time during the study if triggered by AEs or if deemed necessary by the investigator or healthcare provider.

^k All standard 12-lead ECGs will be performed after the subject has been seated or supine for at least 5 minutes. On the Day 1 and 15 Visits, ECGs will be collected before dosing and 5 hours (± 1 hour) after dosing. At all other visits, ECGs will be collected before dosing (as applicable). ECGs collected on the Day 1 Visit before dosing will be performed in triplicate.

^l Sweat chloride will be measured in all subjects as described in [Section 11.4.1](#). If the value cannot be determined from the screening test, a sweat chloride value documented in a laboratory report may be used to establish eligibility. See [Section 8.2.1](#) (Inclusion Criterion #5) for additional detail.

^m At the Period 2 Visit, sweat chloride and ppFEV₁ assessments should be done within 2 hours before TEZ/IVA dosing in the morning.

ⁿ Spirometry may be performed pre- or post-bronchodilator at the Screening Visit. Spirometry will be performed pre-bronchodilator, before the morning dose of study drugs, and should be performed at approximately the same time at every visit. On the Day 1 and Day 15 Visits, spirometry will also be performed 5 hours (± 1 hour) after study drug administration (pre-bronchodilator).

^o For Part D2 subjects only: The ppFEV₁ assessment that will be used for stratification of randomization can be done any time during the Screening Period. See [Section 9.1.2.2](#).

^p *CFTR* genotyping will be performed for all subjects. If the screening *CFTR* genotype result is not received before randomization, a previous *CFTR* genotype laboratory report may be used to establish eligibility. However, as outlined in [Section 9.9](#), subjects who have been randomized and whose screening *CFTR* genotype does not confirm study eligibility must be discontinued from the study, even if a previous *CFTR* genotype laboratory report was used to establish eligibility.

^q FSH will be measured for any potential postmenopausal female subjects with at least 12 months of continuous spontaneous amenorrhea.

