^e To be eligible to continue into the Treatment Period, subjects must have stable CF disease and have remained on stable CF medication regimen during the 28 days before the Day 1 Visit AND must not have had an acute non-CF illness within 14 days before the Day 1 Visit. See [Section 9.1.2.4](#).

^f Randomization may occur on the previous day (Day -1 Visit) after all inclusion and exclusion criteria and criteria for entry into the Treatment Period have been confirmed. See [Section 9.1.2.2.2](#).

^g CFQ-R must be completed before the start of any other assessments scheduled at that visit.

^h The predose assessment on the Day 1 Visit may be performed on the previous day (Day -1 Visit) if randomization has occurred.

ⁱ Weight and height will be measured with shoes off.

^j Vital signs and pulse oximetry will be collected after the subject has been seated for at least 5 minutes.

^k Complete and abbreviated PEs are described in [Section 11.7.3](#). Symptom-targeted PEs will occur at any time during the study if triggered by AEs or if deemed necessary by the investigator or healthcare provider.

Table 3-7 Study VX16-445-001: Schedule of Assessments for Part E

Event/Assessment ^a	Screening	Run-in Period		Treatment Period: Period 1			Washout Period		ETT Visit ^b	Safety Follow-up 28 (± 7) Days After Last Dose ^c
	Days -56 to -29	Day -28 (± 1 day)	Day -14 ^d (+ 13 days)	Day 1 ^e	Day 15 (± 2 days)	Day 29 (± 2 days)	Day 43 (± 3 days)	Day 57 (± 3 days)		
Standard 12-lead ECG ^l	X	X		X	X	X	X	X	X	X
Sweat chloride ^{h,m}	X		X	X	X	X	X	X	X	
Spirometry ⁿ	X ^o		X ^o	X	X	X	X	X	X	X
Urinalysis ^h	X	X		X	X	X	X	X	X	X
Pregnancy test (all females of childbearing potential)	Serum	Urine		Urine		Urine		Urine	Serum	Serum
CFTR genotype ^p	X									
FSH ^q	X									
G6PD activity test ^r	X									

^l All standard 12-lead ECGs will be performed after the subject has been seated or supine for at least 5 minutes. On the Days 1 and 15 Visits, ECGs will be collected before dosing and 5 hours (± 1 hour) after dosing. At all other visits, ECGs will be collected before dosing (as applicable). ECGs collected on the Day 1 Visit before dosing will be performed in triplicate.

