^b If the subject prematurely discontinues study drug treatment, an ETT Visit should be scheduled as soon as possible after the decision to terminate study drug treatment. Subjects who prematurely discontinue treatment will be required to complete the Safety Follow-up Visit. If the ETT Visit occurs 3 or more weeks after the last dose of study drug, the ETT Visit will replace the Safety Follow-up Visit, and a separate Safety Follow-up Visit will not be required.

^c To be eligible to continue into the Treatment Period, subjects must have stable CF disease and have remained on stable CF medication regimen during the 28 days before the Day 1 Visit AND must not have had an acute non-CF illness within 14 days before the Day 1 Visit. See [Section 9.1.2.4](#).

^d The laboratory assessment may be collected at the clinic, at a local laboratory, or during a visit by a qualified individual (e.g., home nurse). If the laboratory assessment is not collected at the clinic, a telephone call to the clinic is required for the collection of AEs. When the laboratory assessment is done in the clinic, the AE collection will also occur in the clinic.

^e Randomization may occur on the previous day (Day -1 Visit) after all inclusion and exclusion criteria have been confirmed.

^f CFQ-R must be completed before the start of any other assessments scheduled at that visit.

^g The predose assessment on the Day 1 Visit may be performed on the previous day (Day -1 Visit) if randomization has occurred.

^h Weight and height will be measured with shoes off.

ⁱ Vital signs and pulse oximetry will be collected after the subject has been seated for at least 5 minutes.

Table 3-8 Study VX16-445-001: Schedule of Assessments for Part F (if Conducted)

Event/Assessment ^a	Screening	Treatment Period: Period 1				ETT Visit ^b	Safety Follow-up 28 (± 7) Days After Last Dose
	Days -28 to -1	Day 1 ^c	Day 8 ^d (± 1 day)	Day 15 (± 2 days)	Day 29 (± 2 days)		
Physical examination ^j	Complete	Abbrev.		Abbrev.	Abbrev.	Abbrev.	Complete
Standard 12-lead ECG ^k	X	X		X	X	X	X
Sweat chloride ^{g, l}	X	X		X	X	X	X
Spirometry ^m	X ⁿ	X		X	X	X	X
Urinalysis ^g	X	X		X	X	X	X
Pregnancy test (all females of childbearing potential)	Serum	Urine			Urine	Serum	Serum
CFTR genotype ^o	X						
FSH ^p	X						
G6PD activity test ^q	X						
Serum chemistry and hematology ^g	X	X	X	X	X	X	X

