9.1.2.7 Early Termination of Treatment (Parts D, E, and F)

If a subject prematurely discontinues treatment, an Early Termination of Treatment (ETT) Visit should be scheduled as soon as possible after the decision to terminate study drug treatment. All subjects who prematurely discontinue treatment (other than those who re-enroll in

Study 661-110, as described in [Section 9.1.2.6](#)) will also be required to complete the Safety Follow-up Visit, approximately 28 days after their last dose of study drug.

If the ETT Visit occurs 3 weeks or later following the last dose of study drug, the ETT Visit will replace the Safety Follow-up Visit, and a separate Safety Follow-up Visit will not be required.

If a subject withdraws from the study and also withdraws consent for disclosure of future information, no further evaluations should be performed and no additional data should be collected. Vertex may retain and continue to use any data and samples collected before such withdrawal of consent.

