8.3 Efficacy Analysis

All efficacy analyses described in this section will be based on the FAS, unless otherwise specified.

The analysis will include all available measurements through the last scheduled on-treatment visit including measurements after treatment discontinuation, per the visit windowing rules described in [Appendix B](#). Except the sensitivity analyses, the post-dose measurements on the same day (e.g. days when spirometry is repeated pre- and post-dose) will not be used for any model-based analyses, but only reported in descriptive safety analyses.

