8.3.2 Analysis of Secondary Efficacy Variables

The secondary efficacy variables include:

- Relative change in ppFEV₁ from baseline through Day 29
- Absolute change in Cystic Fibrosis Questionnaire-Revised (CFQ-R) respiratory domain score from baseline at Day 29

8.3.2.1 Relative change in ppFEV₁ from baseline through Day 29 (Parts D , E and F)

The relative change in ppFEV₁ from baseline through Day 29 is defined in [Section 8.1](#). Analysis of this variable will be based on an MMRM model, similar to the primary analysis of the primary efficacy variable in Parts D, E and F. The tabular presentation of results will also be similar.

8.3.2.2 Absolute change in the CFQ-R respiratory domain score from baseline at Day 29 (Parts D, E and F)

The absolute change in the CFQ-R respiratory domain score from baseline at Day 29 will use the 'Adolescents and Adults' Version for ages 14 and above at baseline, and will be based on the *CFQ-R scaled scores*, as described in [Appendix F](#). Analysis of this variable will be based on an MMRM model, similar to the analysis of the primary efficacy variable in Parts D, E and F. Sex, the continuous baseline ppFEV₁, and the continuous baseline CFQ-R respiratory domain score will be used as covariates in Parts D, E and F. The presentation of results will also be similar.

Part E: Washout Period

In Part E, a supportive analysis will be based on fitting an ANCOVA model to the CFQ-R respiratory domain score Day 57 Visit during Washout Period, using the randomized group in Period 1, as a fixed effect. Sex, continuous baseline ppFEV₁, and continuous baseline CFQ-R respiratory domain score will be used as covariates.

The tabular presentation of results for the average treatment effect across visits will be similar to the primary analysis of the primary efficacy variable for all parts. The adjusted mean (with 95% CI) obtained from the model-based analysis at each post-baseline visit will be plotted by randomized group for each part.

In addition, a waterfall plot showing the subject-level absolute change in CFQ-R at Day 29 will be presented, by treatment group, for each part.

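### CFQ-R is the only modelled efficacy or PD endpoint not collected at the ETT Visit, so an early stop can leave no Day 29 CFQ-R unless the subject keeps scheduled visits that the protocol does not clearly require

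*SAP*

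**What the plan says.** The efficacy rule in SAP section 8.3 reads: "The analysis will include all available measurements through the last scheduled on-treatment visit including measurements after treatment discontinuation". Measurements are placed by the visit windows in SAP Appendix B, Table 11-4.

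The change in CFQ-R respiratory domain score at Day 29 is a secondary endpoint. SAP section 8.3.2.2 says: "Analysis of this variable will be based on an MMRM model, similar to the analysis of the primary efficacy variable". Its covariates are sex, baseline ppFEV₁ and baseline CFQ-R respiratory score. The primary model (SAP section 8.3.1.1.1) assumes data lost through discontinuation are missing at random and imputes nothing.

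After a premature stop, protocol section 9.1.2.7 says the ETT "Visit should be scheduled as soon as possible after the decision to terminate study drug treatment", and that the subject must also complete Safety Follow-up, which a late ETT Visit can replace. It does not mention the remaining Day 15 or Day 29 visits. Two other places bear on them. Section 9.9 says that subjects withdrawn from study drug stay on study where possible. Footnote a of protocol Tables 3-6, 3-7 and 3-8 provides for visits at which no drug is given because the subject has stopped early.

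**The concern.** The plan intends to use data after discontinuation, and for ppFEV₁ and sweat chloride it schedules an assessment at the visit triggered by the stop. For CFQ-R it schedules nothing at either visit named in section 9.1.2.7, and no reason is given for the difference.

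If a subject attends only those two visits, CFQ-R information ends at the stop. A subject who stops before Day 15 is in the FAS but absent from the CFQ-R model. One who stops between Day 15 and Day 29 contributes only through Day 15, under missing at random, with no questionnaire near the stop. Protocol section 12.3.3.1 leaves sensitivity analyses for discontinuation to the SAP. The only one there (section 8.3.1.2) replaces a missing pre-dose Day 15 ppFEV₁ with the post-dose value and does not touch CFQ-R. A questionnaire not completed at the time cannot be recovered.

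**Working it through.** No figure in the plan needs reproducing. The check sets the schedules, discontinuation rules and analysis windows side by side.

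**1. What is collected at ETT**

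| Part (protocol table; SAP table) | CFQ-R collected at | Spirometry at ETT | Sweat chloride at ETT |
|---|---|---|---|
| D1 and D2 (3-6; 11-1) | Days 1, 15, 29 | yes | yes |
| E (3-7; 11-2) | Days 1, 15, 29, 57 | yes | yes |
| F (3-8; 11-3) | Days 1, 15, 29 | yes | yes |

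ETT collection is therefore 0 of 3 parts for CFQ-R, 3 of 3 for spirometry and 3 of 3 for sweat chloride. As a check on column position, Table 3-6 has eight visit columns and its sweat chloride row has eight marks: "Sweat chloride ^{g,l} X X X X X X ^m X X". CFQ-R is also absent from Safety Follow-up in all three parts.

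**2. Which endpoints are modelled**

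They are absolute and relative change in ppFEV₁ (SAP sections 8.3.1.1.1 and 8.3.2.1), the CFQ-R respiratory domain (8.3.2.2) and sweat chloride (8.3.5.1 and 8.3.5.2). CFQ-R is the only one without an ETT assessment.

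**3. What follows for a subject who stops**

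- Stop before Day 15, with only ETT and Safety Follow-up attended: no post-baseline CFQ-R, so no contribution to the model.
- Stop after the Day 15 Visit and before Day 29, with only ETT and Safety Follow-up attended: Day 15 CFQ-R present, Day 29 missing.
- Stop at any time, with scheduled visits kept: CFQ-R is due at the remaining Day 15 and Day 29 visits, and neither loss occurs.
- Stop after the Day 29 Visit (Part D Period 2 or Part E Washout): the Day 29 CFQ-R already exists.

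**4. What a CFQ-R at ETT would supply**

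In SAP Table 11-4 the CFQ-R Day 15 window is study days 2 to 22. The Day 29 window is days 23 to 47 in Part D and 23 to 43 in Parts E and F. For efficacy measures, a scheduled-visit value takes precedence within a window.

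- ETT on days 2 to 22, Day 15 Visit not attended: it supplies a Day 15 value, and the subject enters the model.
- ETT by day 22, Day 15 Visit attended: the scheduled value is used and the ETT value is not.
- ETT from day 23, Day 29 Visit not attended: it supplies a Day 29 value.

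**5. Size**

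Planned arm sizes are in the protocol synopsis. SAP section 8.1 pools Parts D1 and D2 for placebo (9 + 2 = 11) and TC-mid (12 + 6 = 18). One subject lost from the model is:

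- 1/6 = 16.7% of the Part E or Part F control arm
- 1/9 = 11.1% of TC-low
- 1/11 = 9.1% of pooled Part D placebo
- 1/18 = 5.6% of TC-high (Part D or E), TC2-high (Part F) or pooled TC-mid

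**The case against.** The strongest reply is that nothing need be lost. Section 9.9 keeps withdrawn subjects on study where possible, footnote a foresees visits without dosing after a stop, and SAP section 8.3 makes room for the data. Section 9.1.2.7 says Safety Follow-up is also required; it does not cancel other visits. This stands as far as it goes. A reader might infer that every early stop loses its Day 29 CFQ-R, and the documents do not support that. They permit the visits without clearly requiring them.

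A reader might also see a contradiction between SAP section 8.3 and the schedules. There is none: a commitment to use available measurements is not a commitment to collect more.

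The contrast with the other endpoints can be overdrawn too. An ETT spirometry or sweat chloride value does not always enter the model. In Part D1, a value on study days 2 to 12 falls in the Day 8 window, which SAP section 8.3.1.1.1 excludes from the Part D ppFEV₁ model. An ETT value by day 22 also yields to an attended Day 15 Visit.

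Finally, a reader might multiply an assumed stopping rate by an assumed deficit to get a bias in CFQ-R points. The documents give neither input. That product also describes a raw completer mean, whereas the planned MMRM uses baseline covariates and any Day 15 values. Bias in the between-arm comparison would depend on how stopping differs between arms.

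**Conclusion.** The point holds in conditional form. That CFQ-R alone is missing at ETT is confirmed in all three parts. The loss of Day 29 data, or of all post-baseline CFQ-R, depends on two conditions: the stop comes before the corresponding visit, and the subject does not keep the scheduled visits off drug. The protocol leaves the second condition unclear.

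The supportable size is the weight of one affected subject, 5.6% to 16.7% of an arm at the planned sizes. How many subjects would be affected, and in which direction the comparison would move, cannot be derived from the documents. This concerns a secondary endpoint without multiplicity control (SAP section 8.3.2.3) and leaves the primary ppFEV₁ analysis intact. It is worth correcting because the change is cheap and the missing data cannot be recovered.

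**What to change.** 1. **Main remedy for the Day 29 endpoint.** State in protocol section 9.1.2.7 that subjects who stop treatment but remain on study complete the Day 15 and Day 29 efficacy assessments, including CFQ-R, where possible. Align the wording with section 9.9 and footnote a.

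2. **Supplement.** Mark CFQ-R at ETT in protocol Tables 3-6, 3-7 and 3-8 and SAP Tables 11-1 to 11-3, completed before the other assessments at that visit. Use it through the existing windows in SAP Table 11-4. Note that it gives a Day 29 value only from study day 23, and otherwise a Day 15 value when the Day 15 Visit was not attended. It does not help a subject who attended Day 15 and has the ETT Visit by day 22, which is why item 1 comes first.

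The cost is one 50-question form at a visit already scheduled, up to two extra attendances for each subject who stops early and stays on study, and short edits to the protocol and SAP. The CFQ-R windows need no change.

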8.3.1 Primary Efficacy Variable

The primary efficacy variable is the absolute change from baseline in pre-dose percent predicted FEV₁ (ppFEV₁ in percentage units) through Day 29 in Parts D, E and F.

The percent predicted FEV₁ is the ratio of FEV₁ (L) to the predicted FEV₁ (L), expressed as a percentage. The predicted FEV₁ will be calculated using the Quanjer GLI-2012 Regression Equations and Lookup Tables, adjusting for age, height, sex and ethnicity. Details are provided in [Appendix E](#).

8.3.1.1 Primary Analysis of the Primary Efficacy Variable

8.3.1.1.1 Parts D, E and F

The null hypothesis to be tested is that the mean absolute within-group change from baseline in percent predicted FEV₁ (ppFEV₁) through Day 29 is zero for VX-445 in triple combination (TC) with TEZ/IVA in Parts D and E, or with VX-561 in Part F, separately. A 2-sided *p*-value of 0.05 or less will be interpreted as sufficient evidence to reject the null hypothesis.

The primary analysis will be performed using a mixed-effects model for repeated measures (MMRM) with change from baseline in ppFEV₁ as the dependent variable for each part, separately. For Part D, the analysis will include 4 treatment groups: placebo, TC-low, pooled TC-mid, and TC-high. For Part E, the analysis will include 2 treatment groups: placebo + TEZ/IVA, and TC-high (VX-445/TEZ/IVA). For Part F, the analysis will include 2 treatment groups: placebo and TC2-high (VX-445/TEZ/VX-561). The model will include treatment group, visit, and treatment-by-visit interaction as fixed effects and subject as a random effect, with the continuous baseline ppFEV₁ as a covariate, and will include all data from each treatment group and visit during Period 1 in the analysis. The model will be estimated using restricted maximum likelihood. Denominator degrees of freedom for the F test for fixed effects will be estimated using the Kenward-Roger approximation. An unstructured covariance structure will be used to model the within-subject errors. If the model estimation does not converge, a reduced compound symmetry covariance structure will be used instead. Conditional on the observed data and covariates, missing ppFEV₁ data due to treatment or study discontinuation will be assumed to be missing at random; consequently, no imputation of missing data will be performed.

The adjusted means and 95% confidence intervals (CI) of the average treatment effect through Day 29 (Day 15 and Day 29 only) for each triple combination, with a 2-sided *p*-value will be estimated within MMRM using PROC MIXED in SAS, for all within-treatment and between-treatment comparisons, for each part, separately. Contrasts based on the fixed effects in the model, defined at the baseline covariate mean for the combined treatment groups using unique subjects in the FAS who have at least one post-baseline measurement through Day 29, will be used to estimate the average treatment effect across post-baseline visits through Day 29. Day 8 data will not be included in the model for the through Day 29 analysis for Part D.

Further, the adjusted mean and 95% CI of the treatment difference between each triple combination and placebo or TEZ/IVA at each post-baseline visit through Day 29 will be provided along with the corresponding *p*-value, for each part. In addition, the adjusted mean and 95% CI of the within-treatment difference at each post-baseline visit through Day 29 for each treatment group will be provided along with the *p*-value, for each part.

The adjusted mean (with 95% CI) obtained from the MMRM analysis at each post-baseline visit through Day 29 will be plotted by treatment group, for each part. In addition, a waterfall plot showing the subject-level absolute change in ppFEV₁ at Day 29 will be presented, by treatment group.

In addition, for each part, descriptive analyses of the change from baseline will be performed using pre-dose records for all treatment groups by post-baseline visit through the safety follow-up visit.

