12.3.3 Efficacy Analysis (Parts D, E, and F Only)

12.3.3.1 Analysis of Primary Variables

The primary efficacy variable is the absolute change from baseline for ppFEV₁ through Day 29 in Parts D, E, and F. The analysis will be performed using a mixed-effects model for repeated measures (MMRM) with change from baseline as the dependent variable. The model will include treatment group, visit, and treatment-by-visit interaction as fixed effects, subject as random effect, and the continuous baseline ppFEV₁ as a covariate. The model will be estimated using restricted maximum likelihood. Denominator degrees of freedom for the F test for fixed effects will be estimated using the Kenward-Roger approximation. An unstructured covariance structure will be used to model the within-subject errors. If the model estimation does not converge, a compound symmetry covariance structure will be used. Conditional on observed data and covariates, missing data due to treatment or study discontinuation will be assumed to be missing at random.

Adjusted means and 95% confidence intervals of the average treatment effects through Day 29, as applicable, with 2-sided *P* values, will be estimated within MMRM using LSMeans via PROC MIXED in SAS, for all within-group and between-group comparisons in both parts.

Sensitivity analyses for handling missing data due to treatment or study discontinuation will be described in the SAP.

Additional supportive analyses utilizing the Washout Period in Part E to compare treatment groups will be described in the SAP. Subgroup analyses will also be described in the SAP.

There will be no multiplicity adjustment for performing multiple hypothesis tests.

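### The primary MMRM adds a random subject effect to an unstructured within-subject covariance. The term is redundant and can trigger the compound-symmetry fallback for a purely numerical reason.

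*SAP*

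**What the plan says.** SAP 8.3.1.1.1 lists, for the primary model, "treatment-by-visit interaction as fixed effects and subject as a random effect". It then says: "An unstructured covariance structure will be used to model the within-subject errors". Protocol 12.3.3.1 has the same pairing: "subject as random effect, and the continuous baseline ppFEV₁ as a covariate", again with unstructured within-subject errors. SAP 8.3.5.1 repeats both elements for the sweat chloride dose-response test, to be run in PROC GLIMMIX. Protocol 12.3.4 describes that sweat chloride model without a random subject effect.

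The through-Day-29 effect averages Day 15 and Day 29. For Part D the SAP adds: "Day 8 data will not be included in the model for the through Day 29 analysis for Part D". The rule for changing the covariance model is: "If the model estimation does not converge, a reduced compound symmetry covariance structure will be used instead". No other trigger is given.

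Several further models are defined as similar to the primary one: the sensitivity analysis (SAP 8.3.1.2), the Part E washout models (8.3.1.3.2 and 8.3.5.3), relative change in ppFEV₁ (8.3.2.1), CFQ-R (8.3.2.2) and the sweat chloride MMRM (8.3.5.2). Neither document gives SAS code for the covariance, or says that the subject term only names the repeated-measures unit.

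**The concern.** An unstructured covariance already has a free parameter for every variance and covariance between visits. A random subject intercept adds one constant to all of them, which the unstructured part can absorb exactly. The data therefore cannot separate the subject variance from the residual covariance, and the information matrix for the covariance parameters is singular.

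What is at stake is control of the analysis rather than bias. An optimiser given a singular problem may stop without converging, and by the SAP's rule that changes the covariance structure. Whether it stops depends on the software and the programmer's options. For the interim analyses at 50% of Day 15 visits, SAP 9.1.1 has blinded staff write the code on dummy spirometry and sweat chloride data, and an unblinded group run it on the real data. A convergence failure could then first appear in unblinded hands.

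**Working it through.** The plan states no figure for the covariance model, so there is none to reproduce. Its power statement (18 per group, 7 points) gives no SD and plays no part here.

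**1. Parameter count.** Let V be a subject's marginal covariance, R the residual covariance, g the subject variance and J a matrix of ones, so V = R + gJ. With t visits, V has t(t+1)/2 distinct elements.

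- Unstructured plus random subject, t = 2: 3 + 1 = 4 parameters for 3 elements (rank 3).
- Compound symmetry plus random subject: 2 + 1 = 3 parameters for 2 distinct elements (rank 2).
- Unstructured plus random subject, t = 3: 7 for 6; t = 4: 11 for 10. The surplus is always one, so the two-visit restriction is not the cause.

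**2. What is and is not identified.** Replacing (R, g) by (R − cJ, g + c) leaves V unchanged. This was checked on simulated data with the planned group sizes: Part D 11, 9, 18, 18 (placebo 2 + 9; TC-low 9; TC-mid 6 + 12; TC-high 18), and Parts E and F 6 and 18. Assumed variances were 64 (Day 15) and 81 (Day 29), with covariance 45. In the complete-data Part D example, −2 REML log-likelihood was 528.046 and the within-group SE 1.8757 for c = 0, 10, 20 and 40, the same as for unstructured alone. The smallest Hessian eigenvalue was 1.5 × 10⁻¹⁰; the next was 0.011.

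**3. Kenward-Roger.** The flat direction does not change V, so a generalised inverse gives the same correction. Under the same assumed variances and 10% missing at Day 29, unstructured with and without the random effect agreed:

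- Part D: average SE 1.819, df 50.4; Day 29 SE 2.161, df 49.0.
- Parts E/F: average SE 1.811, df 21.0; Day 29 SE 2.125, df 21.1.

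**4. Convergence.** A simple Fisher-scoring REML routine was run on 200 simulated data sets per layout.

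| Model and inversion | Part D | Parts E/F |
|---|---|---|
| Unstructured alone | 200/200 | 200/200 |
| With random subject, plain inverse | 22/200 | 22/200 |
| With random subject, generalised inverse | 194/200 | 180/200 |

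The routine counted any step outside the parameter space as a failure. These counts show dependence on the algorithm; they do not estimate failure rates in SAS.

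**5. Effect of the fallback.** With complete data, compound symmetry replaces both visit variances by roughly their mean. For assumed variances 64 and 81 that is (64 + 81)/2 = 72.5, so the Day 29 SE is multiplied by about √(72.5/81) = 0.946. The variance of the two-visit average, (V₁₁ + 2V₁₂ + V₂₂)/4, depends on the sum of the variances and so hardly moves. Within-group SEs for a group of 18 in four simulated examples:

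| Example | Estimated variance, Day 15 / Day 29 | Average SE, unstructured → CS | Day 29 SE, unstructured → CS |
|---|---|---|---|
| Part D, complete | 55.3 / 90.7 | 1.876 → 1.870 (−0.3%) | 2.246 → 2.010 (−10.5%) |
| Part D, 10% missing | 44.9 / 67.2 | 1.571 → 1.565 (−0.4%) | 1.932 → 1.758 (−9.0%) |
| E/F, complete | 64.8 / 81.9 | 1.803 → 1.804 (+0.05%) | 2.138 → 2.024 (−5.3%) |
| E/F, 10% missing | 124.4 / 88.5 | 2.237 → 2.256 (+0.8%) | 2.253 → 2.485 (+10.3%) |

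The sign follows whichever visit has the larger estimated variance.

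**The case against.** The best defence is that the phrase is loose wording for subject as the repeated-measures unit. Protocol 12.3.4 supports this by omitting the random effect from the sweat chloride model, and the Part E washout models list only fixed effects and covariates. That may well be the intent. But the random effect is written out in SAP 8.3.1.1.1, SAP 8.3.5.1 and Protocol 12.3.3.1, nothing limits its meaning, and for sweat chloride the two documents disagree.

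The second defence is that no inferential quantity is lost when the fit succeeds. That stands in full, for Kenward-Roger as well. A reader might infer that the primary estimate is biased or that its degrees of freedom are invalid; steps 2 and 3 show otherwise.

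A reader might also infer that the model must fail in SAS. That is not established: PROC MIXED was not run, and with a generalised inverse most fits converged. A singular Hessian alone is also not the SAP's trigger; only non-convergence is. Finally, a reader might infer that the fallback always understates the Day 29 SE. In one of the four examples it overstated it.

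**Conclusion.** Wrong as written, but minor. The random subject effect is redundant in the primary model, in the sweat chloride dose-response model and in every model that inherits the specification, and it is equally redundant under the fallback. This rests on algebra alone.

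The consequence is conditional. The choice between unstructured and compound symmetry can turn on software behaviour with no reason in the data; how often is unknown. If it does, the primary Day 15/29 average is nearly unaffected (SE change under 1% in the examples). The Day 29 by-visit SEs can move by about 5 to 11% in either direction under the assumed variances; the documents give no SD. The same mechanism applies to CFQ-R, whose secondary endpoint is at Day 29, but its variances were not examined, so the size there is carried over by analogy.

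**What to change.** Delete the random subject effect from SAP 8.3.1.1.1 and 8.3.5.1, from the models described as similar, and from Protocol 12.3.3.1. This also brings SAP 8.3.5.1 into line with Protocol 12.3.4 on that point. If the protocol is not being amended, record the change in SAP 2.1.

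Model the within-subject covariance through the residual only:

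- PROC MIXED: `REPEATED visit / SUBJECT=subject TYPE=UN`
- PROC GLIMMIX, which has no REPEATED statement: `RANDOM visit / SUBJECT=subject TYPE=UN RESIDUAL`

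Use `TYPE=CS`, without a random effect, as the fallback. State that it applies only when this unstructured model fails to converge, and say whether a Hessian warning counts as failure.

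The cost is a few clauses and the matching code, before the data cut for the first interim analysis. Every estimate from a successful unstructured fit is unchanged, so there is no downside.
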